LL, UL for percentage = Exact 95% Lower and Upper confidence limits

Temperature is reported over 14 days post Dose 3

Template 36 Maximum temperature reported during the <7>-day (Days 1-<7>) post-vaccination period (<Dose 1>), per study group (Exposed Set)

Characteristics	Categories	Coad N =				RTS,S N =				Control N =			
		n	%	LL	UL	n	%	LL	UL	n	%	LL	UL
Maximum temperature	No fever												
	[37.5-38.0]												
	[38.1-38.5]												
	[38.6-39.0]												

Coad =

RTS,S =

Control =

N = number of subjects

n = number of subjects in a given category

% = n / Number of subjects with available results x 100

LL, UL for percentage = Exact 95% Lower and Upper confidence limits

Template 37 Percentage of subjects reporting unsolicited adverse events classified by MedDRA Primary System Organ Class and Preferred Term over 30 days (Days 1-30) post vaccination, per study group (Exposed Set)

Coad =

RTS, S =

Control =

At least one symptom = at least one symptom experienced (regardless of the MedDRA Preferred Term)

N = number of subjects with at least one administered dose

n/% = number/percentage of subjects reporting the symptom at least once

NP = Number percentage of subjects reporting the symptom at least once
 95% CI = exact 95% confidence interval; LL = Lower Limit, UL = Upper Limit

Unsolicited adverse events are reported over 42 days post Dose 3.

Unsolicited adverse events are reported over 42 days post-Dose 3.

Template 38 Percentage of subjects reporting Serious Adverse Events (SAEs) classified by MedDRA Primary System Organ Class and Preferred Term within 30 days post vaccination, per study group, Month 4.5 (Exposed Set)

Coad =

RTS,S =

Control =

At least one symptom = at least one symptom experienced (regardless of the MedDRA Preferred Term)

N = number of subjects with at least one administered dose

n/% = number/percentage of subjects reporting the symptom at least once

95% CI = exact 95% confidence interval; LL = Lower Limit, UL = Upper Limit

Template 39 Percentage of subjects with fatal SAEs classified by MedDRA Primary System Organ Class and Preferred Term within 30 days post vaccination, per study group, Month 4.5 (Exposed Set)

		Coad N =				RTS,S N =				Control N =			
		95% CI				95% CI				95% CI			
Primary System Organ Class (CODE)	Preferred Term (CODE)	n	%	LL	UL	n	%	LL	UL	n	%	LL	UL
At least one symptom													

Coad =

RTS,S =

Control =

At least one symptom = at least one symptom experienced (regardless of the MedDRA Preferred Term)

N = number of subjects with at least one administered dose

n/% = number/percentage of subjects reporting the symptom at least once

95% CI= exact 95% confidence interval; LL = Lower Limit, UL = Upper Limit

Template 40 Percentage of subjects reporting SAEs with causal relationship to vaccination classified by MedDRA Primary System Organ Class and Preferred Term within 30 days post vaccination, per study group, Month 4.5 (Exposed Set)

		Coad N =				RTS,S N =				Control N =			
		95% CI				95% CI				95% CI			
Primary System Organ Class (CODE)	Preferred Term (CODE)	n	%	LL	UL	n	%	LL	UL	n	%	LL	UL
At least one symptom													

Coad =

RTS,S =

Control =

At least one symptom = at least one symptom experienced (regardless of the MedDRA Preferred Term)

N = number of administered doses

n/% = number/percentage of doses with the symptom

95% CI = exact 95% confidence interval; LL = Lower Limit, UL = Upper Limit

Template 41 Listing of SAEs reported until Month 4.5 visit, per study group (Exposed Set)

Group	Sub. No.	Case Id	Age at onset (Year)	Sex	Verbatim	Preferred term	System Organ Class	MA type	Dose	Day of onset	Duration	Causality	Outcome

Coad =

RTS,S =

Control =

Template 42 Incidence of seizures by diagnostic certainty level within 7 days (1-7) post vaccination overall doses (Diagnostic certainty 1-5), per study group (Exposed Set)

		Coad N =				RTS,S N =				Control N =			
				95% CI				95% CI				95% CI	
Characteristics	Categories	n	n/1000	LL	UL	n	n/1000	LL	UL	n	n/1000	LL	UL
Generalized convulsive seizure	Level 1 to 3												
Convulsive seizure	Level 1 to 5												
Diagnostic certainty level	Level 1												
	Level 2												
	Level 3												
	Level 4												
	Level 5												

Coad =

RTS,S =

Control =

Total = Total

N = number of doses

n = number of doses in a given category

n/1000 = n / Number of doses with available results x 1000

LL, UL for percentage = Exact 95% Lower and Upper confidence limits

Level 1: Witnessed sudden loss of consciousness AND generalized, tonic, clonic, tonic-clonic, or atonic motor manifestations

Level 2: History of unconsciousness AND generalized, tonic, clonic, tonic-clonic, or atonic motor manifestations

Level 3: History of unconsciousness AND other generalized motor manifestations

Level 4: Reported generalized convulsive seizure with insufficient evidence to meet the case definition

Level 5: Not a case of generalized convulsive seizure

Within 14 days post Dose 3

Template 43 Incidence of seizures by diagnostic certainty level and history of fever within 7 days (1-7) post vaccination overall doses (Diagnostic certainty 1-5), per study group (Exposed Set)

		Coad N =				RTS,S N =				Control N =			
				95% CI				95% CI				95% CI	
Characteristics	Categories	n	n/1000	LL	UL	n	n/1000	LL	UL	n	n/1000	LL	UL
Level 1	History of fever												
	No history of fever												
Level 2	History of fever												
	No history of fever												
Level 3	History of fever												
	No history of fever												
Level 4 and 5	History of fever												
	No history of fever												

Coad =

RTS,S =

Control =

Total = Total

N = number of generalized convulsive seizures

n = number of generalized convulsive seizures in a given category

% = n / Number of generalized convulsive seizures with available results x 100

LL, UL for percentage = Exact 95% Lower and Upper confidence limits

Level 1: Witnessed sudden loss of consciousness AND generalized, tonic, clonic, tonic-clonic, or atonic motor manifestations

Level 2: History of unconsciousness AND generalized, tonic, clonic, tonic-clonic, or atonic motor manifestations
 Level 3: History of unconsciousness AND other generalized motor manifestations
 Level 4: Reported generalized convulsive seizure with insufficient evidence to meet the case definition
 Level 5: Not a case of generalized convulsive seizure
 Within 14 days post Dose 3

Template 44 Incidence of seizures by diagnostic certainty level and fever within 7 days (1-7) post vaccination overall doses (Diagnostic certainty 1-5), per study group (Exposed Set)

		Coad N =				RTS,S N =				Control N =			
				95% CI				95% CI				95% CI	
Characteristics	Categories	n	n/1000	LL	UL	n	n/1000	LL	UL	n	n/1000	LL	UL
Level 1	<38°C												
	≥38°C												
	Missing temperature												
Level 2	<38°C												
	≥38°C												
	Missing temperature												
Level 3	<38°C												
	≥38°C												
	Missing temperature												
Level 4 and 5	<38°C												
	≥38°C												
	Missing temperature												

Coad =

RTS,S =

Control =

Total = Total

N = number of generalized convulsive seizures

n = number of generalized convulsive seizures in a given category

% = n / Number of generalized convulsive seizures with available results x 100

LL, UL for percentage = Exact 95% Lower and Upper confidence limits

Level 1: Witnessed sudden loss of consciousness AND generalized, tonic, clonic, tonic-clonic, or atonic motor manifestations

Level 2: History of unconsciousness AND generalized, tonic, clonic, tonic-clonic, or atonic motor manifestations

Level 3: History of unconsciousness AND other generalized motor manifestations

Level 4: Reported generalized convulsive seizure with insufficient evidence to meet the case definition

Level 5: Not a case of generalized convulsive seizure

Within 14 days post Dose 3

Template 45 Incidence of concomitant medication administered during the <30-day (Days 1-30)> post-vaccination period by dose and overall, per study group (Exposed Set)

	Coad			RTS,S			Control								
				95% CI					95% CI					95% CI	
	N	n	%	LL	UL	N	n	%	LL	UL	N	n	%	LL	UL
Dose 1															
Any antipyretic															
Prophylactic antipyretic															
Dose 2															
Any antipyretic															
Prophylactic antipyretic															
Dose 3															
Any antipyretic															
Prophylactic antipyretic															
Overall/dose															
Any antipyretic															
Prophylactic antipyretic															
Overall/subject															
Any antipyretic															
Prophylactic antipyretic															

Coad =

RTS,S =

Control =

For each dose and overall/subject:

N= number of subjects with at least one administered dose

n/%= number/percentage of subjects who started to take the specified concomitant medication at least once during the mentioned period

For overall/dose:

N= number of administered doses

During the < 42-day> post-vaccination period post Dose 3

Template 46 Number (%) of subjects with serious adverse events including number of events reported during the study period (Exposed Set)

					Coad N =			RTS,S N =			Control N =		
Type of Event	Primary System Organ Class	Preferred Term (CODE)	n*	n	%	n*	n	%	n*	n	%		
SAE	At least one symptom												
	<each SOC>	<each PT term>											
Related SAE	At least one symptom												
	<each SOC>	<each PT term>											
Fatal SAE	At least one symptom												
	<each SOC>	<each PT term>											
Related fatal SAE	At least one symptom												
	<each SOC>	<each PT term>											

Coad =

RTS,S =

Control =

N = number of subjects with the administered dose

n* = number of events reported

n/% = number/percentage of subjects reporting the symptom at least once

Template 47 Solicited and unsolicited symptoms, classified by MedDRA Primary System Organ Class and Preferred Term within the 42-day (Days 1-42) post-vaccination period including number of events - SAE excluded (Exposed Set)

		CoadN =			RTS,S N =			Control N =		
Primary System Organ Class (CODE)	Preferred Term (CODE)	n*	n	%	n*	n	%	n*	n	%
At least one symptom										
<each SOC>	<each PT term>									

Coad =

RTS,S =

Control =

At least one symptom = at least one symptom experienced (regardless of the MedDRA Preferred Term)

N = number of subjects with the administered dose

n* = number of events reported

n/% = number/percentage of subjects reporting the symptom at least once

Template 48 Listing of dropouts due to AEs, SAEs and solicited symptoms (Exposed Set)

Group	Study - Subject	Country	Gender	Race	AE Description	SAE	Causality	Outcome	Type of discontinuation

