- Control: active control (Group receiving the EPI interventions alone [Vitamin A at 6 months and YF vaccine and a combined measles and rubella vaccine at 9 months of age]). Children from this group will receive a 3-dose course (0, 1, 2-month) and a booster dose (17.5 months post Dose 3) of RTS,S/AS01_E from Visit 6 onwards (10.5 months of age) so they can benefit from the same protection as the children from the Coad and the RTS,S groups.
- Vaccination schedules:
 - For the **Coad group**, children will receive Vitamin A and RTS,S/AS01_E vaccine on Day 0 (Visit 2 [6 months of age]), RTS,S/AS01_E alone at Visit 3 (7.5 months of age), co-administration of RTS,S/AS01_E, YF vaccine and a combined measles and rubella vaccine at Visit 4 (9 months of age), and a booster dose of RTS,S/AS01_E at Visit 10 (27 months of age).
 - For the **RTS,S group**, children will receive Vitamin A and RTS,S/AS01_E vaccine on Day 0 (Visit 2 [6 months of age]), RTS,S/AS01_E alone at Visit 3 and 4 (7.5 and 9 months of age), YF vaccine and a combined measles and rubella vaccine at Visit 6 (10.5 months of age), and a booster dose of RTS,S/AS01_E at Visit 10 (27 months of age).
 - For the **Control group**, children will receive Vitamin A on Day 0 (Visit 2 [6 months of age]) and YF vaccine and a combined measles and rubella vaccine at Visit 4 (9 months of age). These children will also receive RTS,S/AS01_E vaccine at Visit 6, 7 and 8 (10.5, 11.5 and 12.5 months of age) and a booster dose of RTS,S/AS01_E vaccine at Visit 12 (30 months of age).
- Treatment allocation: randomized in a 1:1:1 ratio to each study group.
- Blinding: open

Table 3 Blinding of study epoch

Study Epoch	Blinding
Epoch 001	open

- Sampling schedule:
 - For the **Coad group**, blood samples will be taken on Day 0, on the day of co-administration of RTS,S/AS01_E with the YF vaccine and the combined measles

and rubella vaccine (Month 3) and at one month post co-administration (Month 4).

- For the **RTS,S group**, blood samples will be taken on Day 0 and at one month post Dose 3 of RTS,S/AS01_E (Month 4).
- For the **Control group**, blood samples will be taken on Day 0, on the day of administration of the YF vaccine and the combined measles and rubella vaccine (Month 3) and at one month post-vaccination with the YF vaccine and the combined measles and rubella vaccine (Month 4).
- Type of study: self-contained.
- Data collection: Electronic Case Report Form (eCRF).
- Safety monitoring:

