 - For the Control group, the occurrence of solicited general AEs over a 7-day follow-up period (day of administration and 6 subsequent days) after administration of Vitamin A at 6 months of age (Visit 2).
 - For the Coad and the RTS,S groups, the occurrence of solicited local and general AEs over a 7-day follow-up period (day of vaccination and 6 subsequent days) after dose of study vaccines administered at 7.5 months of age (Visit 3).
 - For the Control group, the occurrence of solicited general AEs over a 7-day follow-up period (day of visit and 6 subsequent days) after Visit 3 (7.5 months of age).
 - For all groups, the occurrence of solicited general and local AEs over a 14-day follow-up period (day of vaccination and 13 subsequent days) after dose of study vaccines administered at 9 months of age (Visit 4).
- Unsolicited AEs.
 - For all groups, the occurrence of unsolicited AEs over a 30-day follow-up period (day of administration and 29 subsequent days) after administration of Vitamin A and study vaccines at 6 months of age (Visit 2).
 - For the Coad and the RTS,S groups, the occurrence of unsolicited AEs over a 30-day follow-up period (day of vaccination and 29 subsequent days) after dose of study vaccines administered at 7.5 months of age (Visit 3).
 - For the Control group, the occurrence of unsolicited AEs over a 30-day follow-up period (day of visit and 29 subsequent days) after Visit 3 (7.5 months of age).
 - For all groups, the occurrence of unsolicited AEs over a 42-day follow-up period (day of vaccination and 41 subsequent days) after dose of study vaccines administered at 9 months of age (Visit 4).
 - For the Coad and the RTS,S groups, the occurrence of unsolicited AEs over a 30-day follow-up period (day of vaccination and 29 subsequent days) after the booster dose of study vaccine administered at 27 months of age (Visit 10).
 - For the Control group, the occurrence of unsolicited AEs over a 30-day follow-up period (day of vaccination and 29 subsequent days) after dose of study vaccines administered at 10.5, 11.5, 12.5 and 30 months of age (Visit 6, 7, 8 and 12).

- SAEs: all, fatal and related SAEs.
 - The occurrence of SAEs occurring within 30 days (day of vaccination and 29 subsequent days) after each administration.
 - The occurrence of SAEs from Screening visit (Visit 1) until Month 4.5.
 - The occurrence of SAEs from Screening visit (Visit 1) until study end (Month 33 for Coad and RTS,S groups and Month 36 for the Control group).

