6.5. Analysis of safety

6.5.1. Analysis of safety planned in the protocol

The primary analysis will be based on the ES.

The percentage of subjects with at least one local AE (solicited and unsolicited), with at least one general AE (solicited and unsolicited) and with any AE during the solicited follow-up period [7 days post Dose 1, post Dose 2 and 14 days post Dose 3] will be tabulated with exact 95% CI after each vaccine dose and overall. The percentage of doses followed by at least one local AE (solicited and unsolicited), by at least one general AE (solicited and unsolicited) and by any AE will be tabulated for the overall vaccination course, with exact 95% CI. Similar tables will be generated for Grade 3 AEs and AEs considered as causally related to vaccination.

The percentage of subjects reporting each individual solicited local and general AE during the solicited follow-up period will be tabulated with exact 95% CI. The percentage of doses followed by each individual solicited local and general AE will be tabulated for each dose and for the overall vaccination course, with exact 95% CI. Similar tables will be generated for Grade 3 AEs, causal events and for fever, temperature in 0.5°C increments.

The proportion of subjects reporting an AE (unsolicited) until 30 days (Days 0-29) post each dose of RTS,S/AS01_E, classified by the Medical Dictionary for Regulatory Activities (MedDRA) preferred term level will be tabulated with exact 95% CI. The proportion of subjects reporting an AE (unsolicited) until 42 days (Days 0-41) after the administration of the YF vaccine and the combined measles and rubella vaccine (restricted to the Coad group and Control group), classified by the MedDRA preferred term level will be tabulated with exact 95% CI. Similar tables will be generated for Grade 3 AEs and AEs considered as causally related to vaccination.

The proportion of subjects reporting an SAE (all, fatal, related) occurring within 30 days (day of vaccination and 29 subsequent days) after each visit where a study product is potentially administered, classified by the MedDRA preferred term level will be tabulated with exact 95% CI.

The proportion of subjects reporting an SAE (all, fatal, related) from Day 0 to Month 4.5 and over the whole study duration (Day 0 to Month 33 for Coad and RTS,S groups and Month 36 for the Control group), classified by the MedDRA preferred term level will be tabulated with exact 95% CI.

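### Templates 37 to 40 show no visit blocks for unsolicited AEs and SAEs, and SAP 6.5.1 leaves the RTS,S group out of the 42-day table that SAP 4.2 sets for all groups

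*SAP*

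**What the plan says.** **Endpoints.** SAP 4.2 lists unsolicited AEs as separate endpoints after Visit 2, Visit 3 and Visit 4. The Visit 4 item begins "For all groups, the occurrence of unsolicited AEs over a 42-day follow-up period". The SAE item reads "The occurrence of SAEs occurring within 30 days (day of vaccination and 29 subsequent days) after each administration".

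**Analysis text.** SAP 6.5.1 tabulates unsolicited AEs by preferred term for 30 days after each RTS,S/AS01E dose. It tabulates 30-day SAEs "after each visit where a study product is potentially administered". It also plans a 42-day unsolicited AE table after the yellow fever and measles-rubella vaccines, for Coad and Control only. Protocol 10.9 contains the same restriction.

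**Layouts.** Template 37 (unsolicited AEs by preferred term) is titled "over 30 days (Days 1-30) post vaccination, per study group (Exposed Set" and carries the footnote "Unsolicited adverse events are reported over 42 days post Dose 3". Templates 38 to 40 (all, fatal and related SAEs) are titled "within 30 days post vaccination, per study group, Month 4.5 (Exposed Set". In Templates 37 to 39, "N = number of subjects with at least one administered dose". Template 40 has a title about percentages of subjects, but its footnote makes N the number of administered doses.

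**Design.** Under Protocol 3, Coad and RTS,S receive the same products at Visits 2 and 3. At Visit 4 Coad adds the yellow fever and measles-rubella vaccines, while the RTS,S group has RTS,S/AS01E "alone at Visit 3 and 4 (7.5 and 9 months of age".

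**The concern.** The safety objective (SAP 3.2) compares co-administration with RTS,S/AS01E alone. Among Visits 2 to 4 that contrast exists only at Visit 4. A table that counts a child once if an event follows any of the three visits mixes the visit of interest with two visits at which the groups are treated alike. For common events, many children are already counted from Visits 2 and 3, so an excess after Visit 4 has less room to show.

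The text has a gap of its own. By leaving the RTS,S group out of the 42-day table, SAP 6.5.1 does not serve the all-groups endpoint in SAP 4.2. The only layout shown that gives unsolicited AEs on their own, by preferred term, for the RTS,S group over 42 days after Visit 4 is then Template 37, which appears to be pooled. Template 47 also spans 42 days for all groups, but it mixes solicited with unsolicited symptoms, excludes SAEs and shows no dose split.

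**Working it through.** **1. Is there a dose dimension?**

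- Templates 26 to 34 and 45 say in their titles that they are by dose and overall, and they have dose blocks. Template 36 has a placeholder for the dose.
- Templates 35 and 42 to 44 say that they cover overall doses.
- Templates 37 to 40 say neither. Their footnotes also lack the line, used in Templates 26 to 34, that separates per-dose from overall counts.
- The bodies of Templates 39 and 40 show one set of columns per group and no dose rows. The bodies of Templates 37 and 38 were not readable in the text available, so pooling there is inferred from title, footnote and N.

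**2. Does Visit 6 disturb the contrast?** The RTS,S group receives the yellow fever and measles-rubella vaccines at Visit 6. By Protocol Table 7, Visit 5 is 28 to 42 days after Visit 4, and Visit 6 is 14 to 21 days after Visit 5. Visit 6 is therefore 28 + 14 = 42 to 42 + 21 = 63 days after Visit 4. The unsolicited AE window runs from Day 0 to Day 41, so on-schedule Visit 6 vaccines fall after it.

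**3. Effect of pooling per child.** The documents give no AE or SAE rates, so the rates here are assumptions. Let p be the risk after each visit in both groups, except that Coad has risk q after Visit 4, with independent windows.

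- RTS,S pooled: 1 - (1-p)³
- Coad pooled: 1 - (1-p)²(1-q)
- Difference: (1-p)²(q-p)

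With q = 1.5p:

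| p | q | Visit 4 difference (points) | Pooled, RTS,S vs Coad | Pooled difference (points) | Share kept | Risk ratio, Visit 4 then pooled |
|---|---|---|---|---|---|---|
| 1% | 1.5% | 0.5 | 2.97% vs 3.46% | 0.49 | 98% | 1.50, 1.16 |
| 2% | 3% | 1.0 | 5.88% vs 6.84% | 0.96 | 96% | 1.50, 1.16 |
| 10% | 15% | 5.0 | 27.10% vs 31.15% | 4.05 | 81% | 1.50, 1.15 |
| 30% | 45% | 15.0 | 65.70% vs 73.05% | 7.35 | 49% | 1.50, 1.11 |
| 50% | 75% | 25.0 | 87.50% vs 93.75% | 6.25 | 25% | 1.50, 1.07 |

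A larger SAE effect, 1% against 3%, gives 2.97% against 4.93% pooled. The difference is 1.96 of the original 2.00 points, and the ratio falls from 3.0 to 1.66.

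**4. Sensitivity to independence.** Positive correlation within a child lessens the dilution. At the extreme, where the same children have events after every visit, the pooled risks are p and q and nothing is lost. The share kept then lies between (1-p)² and 1.

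**5. Template 40, if N is doses.** With three vaccination visits per child, the pooled per-dose risks are p for RTS,S and (2p+q)/3 for Coad. The difference is (q-p)/3. Much of this is a change of unit, which is why the unit must be settled first.

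**6. Visibility, for illustration.** Protocol 10.4 gives 205/(1-0.12) = 232.95, rounded up to 233 per group, as stated. At that size, the chance of a two-sided p < 0.05 (two-proportion normal approximation) falls from 0.92 to 0.41 for 30% against 45%, and from 0.37 to 0.16 for 10% against 15%. No such test is planned.

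**The case against.** The strongest reply is that mock tables are not the analysis plan. SAP 6.5.1 governs, and it commits to tabulation per dose and per visit. Annex 3 calls its displays illustrative, to be adapted through a table list (the TFL TOC) that is not among the documents. This stands: it cannot be shown that by-dose versions will be missing. Adaptation cannot be assumed either. The mocks were copied from another study, and Templates 6 and 12 still carry foreign group names and an age criterion of 8 to 12 weeks.

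The footnote on Template 37 does not prove pooling. Templates 32 to 34 and 45 have similar notes on the Dose 3 window and do have dose blocks. The N definition also appears for dose rows elsewhere. This stands too; the inference rests on title, footnote and N together, and on the visible bodies of Templates 39 and 40.

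There is partial cover. The 30-day tabulation in SAP 6.5.1 includes Coad against RTS,S after Dose 3, so the text omits 42 - 30 = 12 days of the RTS,S window. Template 26 gives Dose 3 rows over 7 and 14 days, though with solicited and unsolicited symptoms combined. Template 41 lists each SAE with dose and day of onset, but without percentages or intervals.

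Heavy dilution needs risks of 30 to 50% per visit. Such risks suit the row for any event better than single preferred terms.

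**Conclusion.** The mismatch is real and worth correcting. The endpoints and analysis text are per visit, and Templates 37 to 40 show no visit dimension. The 42-day Visit 4 endpoint covers all groups in SAP 4.2 but two groups in SAP 6.5.1. As a result, nothing shown presents Coad against RTS,S over the full 42 days after Visit 4 without pooling.

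Under independent windows of equal risk, the loss in absolute difference is large for common events and negligible at SAE-like rates, while the ratio shrinks throughout. These sizes rest on assumed rates and on per-child pooling. SAP 7 makes safety comparisons descriptive, so the detection probabilities only show how visible a difference would be.

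A reader might infer three stronger things that the documents do not support:

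- That the per-visit endpoints will not be delivered. SAP 6.5.1 promises them, and the table list is unseen.
- That SAE differences would look much smaller in absolute terms. Counted per child, they would not.
- That Visit 4 is the only visit in the study at which the two groups differ. They also differ at Visit 6.

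**What to change.** 1. Give Templates 37 to 40 blocks for Dose 1 (Visit 2), Dose 2 (Visit 3) and Dose 3 (Visit 4), then overall, for all three groups, with the SAP 4.2 windows. Show the visit in each label, because Control receives no product at Visit 3. Keep the pooled figures only as a summary.
2. In SAP 6.5.1, remove the Coad and Control restriction so that the 42-day unsolicited AE table after Visit 4 covers all three groups. Name it as the table for the Coad versus RTS,S safety objective. Because Protocol 10.9 has the same restriction, record the change in SAP 9.
3. Make the unit in Template 40 agree with its title.

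The cost is small. SAP 4.2 already requires these data for every group, and Annex 3 allows minor layout changes without a SAP amendment; the change to the 6.5.1 text is the only formal edit. The price is longer tables with sparser preferred-term rows.

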The proportion of subjects reporting an AEs of specific interest (pIMDs, meningitis and seizures) from Day 0 to Month 4.5 and over the whole study duration (Day 0 to Month 33 for Coad and RTS,S groups and Month 36 for the Control group), classified by the MedDRA preferred term level will be tabulated with exact 95% CI.

For generalized convulsive seizures occurring within 7 days after vaccines administered at Visit 2 and 3 (Coad and RTS,S groups) and 15 days after vaccines administered at Visit 4 (all groups) an analysis will be performed based on the Brighton Collaborations guidelines [Bonhoeffer, 2004]. This includes descriptive tables of the time relationship of seizures to vaccination, the duration of seizures and the level of diagnostic certainty.

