 - The occurrence of pIMDs from Day 0 until Month 4.5.
 - The occurrence of pIMDs from Day 0 until study end (Month 33 for Coad and RTS,S groups and Month 36 for the Control group).
 - The occurrence of meningitis from Day 0 until Month 4.5.
 - The occurrence of meningitis from Day 0 until study end (Month 33 for Coad and RTS,S groups and Month 36 for the Control group).
 - The occurrence of seizure (occurring within 30 days post-vaccination for vaccine doses administered at 6 and 7.5 months of age [Visits 2 and 3] or 42 days post-vaccination for vaccine doses administered at 9 months of age [Visit 4]) from Day 0 until Month 4.5.
 - The occurrence of seizure occurring within 30 days post-vaccination for vaccine doses administered at 6, 7.5 and 27 months of age (Visits 2, 3 and 10 for Coad and RTS,S group) and at 10.5, 11.5, 12.5 and 30 months of age (Visits 6, 7, 8 and 12 for Control group) or 42 days post-vaccination for vaccine doses administered at 9 months of age (Visit 4 for all groups).
 - The occurrence of generalized convulsive seizure occurring within 7 days after vaccines administered at Visit 2 and 3 (Coad and RTS,S groups) and 14 days after vaccines administered at Visit 4 (all groups).

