The proportion of subjects reporting an AEs of specific interest (pIMDs, meningitis and seizures) from Day 0 to Month 4.5 and over the whole study duration (Day 0 to Month 33 for Coad and RTS,S groups and Month 36 for the Control group), classified by the MedDRA preferred term level will be tabulated with exact 95% CI.

For generalized convulsive seizures occurring within 7 days after vaccines administered at Visit 2 and 3 (Coad and RTS,S groups) and 14 days after vaccines administered at Visit 4 (all groups) an analysis will be performed based on the Brighton Collaborations guidelines [**Bonhoeffer**, 2004]. This includes descriptive tables of the time relationship of seizures to vaccination, the duration of seizures and the level of diagnostic certainty.

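### SAP Template 42 pools seizure rates over doses with unequal risk windows, so they cannot be compared with Control, and a Visit 4 effect is diluted against the RTS,S group

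*SAP*

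**What the plan says.** SAP 6.5.1 sets the analysis population in two parts: "For generalized convulsive seizures occurring within 7 days after vaccines administered at Visit 2 and 3 (Coad and RTS,S groups"), and then "14 days after vaccines administered at Visit 4 (all groups) an analysis will be performed". The endpoint in SAP 4.2 uses the same windows. Control therefore has no seizure window after Visits 2 and 3 in this analysis.

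The mock table for it, SAP Annex 3 Template 42, is titled "Incidence of seizures by diagnostic certainty level within 7 days (1-7) post vaccination overall doses". Its N is a number of doses, and its rate is defined as "n/1000 = n / Number of doses with available results x 1000". A footnote adds "Within 14 days post Dose 3". The table has rows for Brighton certainty levels and none for individual doses.

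Templates 43 and 44 break seizures down by certainty level and fever, also over all doses. Their footnotes make N the number of generalized convulsive seizures, although the column header is still n/1000.

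The Visit 4 window is not consistent across the documents. Protocol 10.2, SAP 4.2 and SAP 6.5.1 give 14 days, while Protocol 10.9 gives "15 days after vaccines administered at Visit 4 (all groups").

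**The concern.** Febrile convulsion is listed in Protocol 1.3.1 as an important identified risk of both RTS,S/AS01E and measles vaccine. Protocol 1.2.3 explains the longer follow-up at Visit 4 by the timing of fever after measles-rubella vaccination (days 5 to 12). Coad and RTS,S children receive the same products at Visits 2 and 3. The measles-rubella and yellow fever vaccines given to the RTS,S group at Visit 6 fall outside the seizure windows. Visit 4 is therefore the only visit in this analysis that can carry a co-administration signal.

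A single rate over all doses does two things. It averages Visit 4 with two visits at which Coad and RTS,S do not differ. It also divides events from windows of different length by a plain count of doses, and the mix of windows differs between Control and the other two groups. A reader of Template 42 could see a lower rate in Coad than in Control with no true difference, or miss a real excess at Visit 4.

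**Working it through.** The documents give no seizure rate, power or sample size for this table, so there is no stated figure to reproduce. The check asks what the pooled rate would show under known truths.

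**Inputs from the documents**
- Windows: 7, 7 and 14 days in Coad and RTS,S; 14 days after Visit 4 in Control (SAP 4.2, 6.5.1).
- Denominator: doses (Template 42).
- Planned size: 233 children per group (Protocol 10.4). With full attendance, that is 3 × 233 = 699 doses in Coad and in RTS,S, and 233 in Control if only Visit 4 counts.

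**Assumptions, not from the documents**
- Constant daily seizure hazard.
- Equal numbers of doses at each visit.
- Co-administration multiplies the Visit 4 hazard by k.

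**Step 1: risk-days per dose.** Coad and RTS,S have (7 + 7 + 14)/3 = 28/3 = 9.33. Control has 14/1 = 14.

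**Step 2: Coad/Control with no effect.** 9.33/14 = 0.67. With the 15-day window of Protocol 10.9 it is ((7 + 7 + 15)/3)/15 = 0.64.

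**Step 3: a Visit 4 effect.** Pooled Coad/RTS,S is (14 + 14k)/28 = (1 + k)/2. Pooled Coad/Control is ((14 + 14k)/3)/14 = (1 + k)/3.

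| True k at Visit 4 | Coad/RTS,S pooled | Coad/Control pooled | Visit 4 only, either comparator |
|---|---|---|---|
| 1 | 1.00 | 0.67 | 1 |
| 2 | 1.50 | 1.00 | 2 |
| 3 | 2.00 | 1.33 | 3 |

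Invented counts make this concrete. Suppose one seizure after each of Visits 2 and 3 in Coad and in RTS,S, and two after Visit 4 in RTS,S and in Control, doubled to four in Coad. The pooled rates per 1000 doses are Coad 6/699 = 8.58, RTS,S 4/699 = 5.72 and Control 2/233 = 8.58. The doubling vanishes against Control and shows as 1.5 against RTS,S. At Visit 4 alone, Coad is 4/233 = 17.17 and each comparator is 2/233 = 8.58, a ratio of 2.

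**Step 4: other hazard shapes.** Let f be the risk after a Visit 2 or 3 dose as a fraction of the comparator's risk after a Visit 4 dose. The null Coad/Control ratio is (2f + 1)/3, and pooled Coad/RTS,S is (2f + k)/(2f + 1).

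| f | Coad/Control, k = 1 | Coad/RTS,S, k = 2 |
|---|---|---|
| 0.25 | 0.50 | 1.67 |
| 0.50 (constant hazard) | 0.67 | 1.50 |
| 0.75 | 0.83 | 1.40 |
| 1.00 | 1.00 | 1.33 |

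**Step 5: other counts of Control doses.** SAP 11.2.2 ties a dose to a visit with vaccination, which points to Visit 4 only. SAP 5.1.2 counts Vitamin A as study treatment, and Template 26 gives Control rows for Doses 1, 2 and 3. Under a constant hazard and no effect, the Coad/Control ratios are:
- Vitamin A visit and Visit 4, events from both: 9.33/(21/2) = 0.89.
- The same two visits in N, Visit 4 events only: 9.33/(14/2) = 1.33.
- Three visits, events from all: 9.33/9.33 = 1.00.
- Three visits in N, Visit 4 events only: 9.33/(14/3) = 2.00.

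The null Coad/RTS,S ratio is 1.00 throughout.

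**The case against.** The strongest reply is that the annex does not control the output. SAP section 13 calls the displays illustrative and open to adaptation. The list of tables sits in a separate document that is not available here, and Templates 35 and 36 show a pooled table paired with a by-dose one. SAP 6.5.1 also promises tables of the time relationship of seizures to vaccination. Seizures within 30 days of Visits 2 and 3 or 42 days of Visit 4 are reported as SAEs, and Template 41 lists SAEs by group with dose and day of onset. The comparison is descriptive (SAP 7), and pooling removes no events: an excess of Visit 4 cases still appears in the count.

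Most of this stands as a limit on the consequence: a careful reader could rebuild part of the Visit 4 comparison. It does not answer the point. Nothing in the SAP text directs a by-visit split for this endpoint, and no mock table gives a Visit 4 rate by Brighton level. The by-visit SAE tables use a 30-day window and preferred terms. The listing has no denominators or certainty levels.

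A reader might go further and infer three things the documents do not support.
- That every comparison with Control is biased against Control. Steps 4 and 5 show null ratios below, at and above 1. The constant hazard is itself doubtful, since Protocol 1.3.1 places the RTS,S febrile convulsion risk within seven days and Protocol 1.2.3 places measles-rubella fever at days 5 to 12.
- That the contrast in the safety objective is biased. Coad and RTS,S share the same windows, so it is diluted only.
- That Templates 43 and 44 have the same fault. With N equal to seizures they are case breakdowns, so the risk-day argument does not reach them.

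**Conclusion.** The point holds for Template 42. Its per-dose rate cannot be read across to Control: under the plainest reading (constant daily hazard, Visit 4 as Control's only dose) the null ratio is 0.67. Under the other cases worked above it runs from 0.50 to 2.00, because the SAP does not define Control's denominator and the hazard shape is unknown. Against RTS,S, the contrast the objective names, there is no bias under the null. A true Visit 4 ratio of 2 appears as 1.5 under a constant hazard (1.33 to 1.67 over the range of f shown), and a ratio of 3 appears as 2.0 under a constant hazard. All of these figures assume equal dose numbers per visit. The weakness lies in how a descriptive safety table is laid out; the underlying data are not lost.

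**What to change.** In SAP 6.5.1 and Template 42:
- Add lead rows for Visit 4 only, with a 14-day window, all three groups, and children vaccinated at Visit 4 as the denominator.
- Show Visits 2 and 3 (7 days) in separate rows for Coad and RTS,S.
- Drop the pooled rate for Control, or state its denominator and give it per child-day at risk.

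In Templates 43 and 44, reconcile the n/1000 header with the footnote that makes N the number of seizures, and split by visit if wanted.

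Reconcile the 7-day title of Template 42 with its 14-day footnote, and the 14-day Visit 4 window (Protocol 10.2, SAP 4.2, SAP 6.5.1) with the 15 days in Protocol 10.9.

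The cost is wording and table shells only, since dose and onset day are already captured. The price is sparser cells: with no events, the exact 95% upper limit is 5.26 per 1000 on 699 doses and 15.71 per 1000 on 233.
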